9.2 CONCOMITANT MEDICATIONS

9.2.2 Additional Guidance to the Investigator

Subjects that receive CYP2D6 substrates with a narrow therapeutic index, such as TCAs, concomitantly with investigational product will require additional oversight by the Investigator. Oversight should include close review of potential adverse events (AEs) associated with CYP2D6 substrates with a narrow therapeutic index and evaluation of untoward events including worsening of psychiatric symptoms. Dose adjustments to concomitant CYP2D6 substrate and/or investigational product should be made based

upon the Investigator's clinical judgement and on the safety, tolerability, and efficacy of the substrate.

The Sponsor will continue to evaluate and discuss Investigator concerns regarding AEs associated with the use or discontinuation of CYP2D6 substrates to ensure protection of subjects enrolled in the 747-302 study.

3. LIST OF ABBREVIATIONS AND DEFINITIONS OF TERMS

The following abbreviations and specialist terms are used in this protocol.

Abbreviation or Specialist Term	Explanation
AE	adverse event
APRI	aspartate aminotransferase to platelet ratio index
CRF	case report form
ELF	enhanced liver fibrosis
EOS	end of study
EOT	end of treatment
FDA	Food and Drug Administration
IB	Investigator's Brochure
OCA	obeticholic acid
PBC	primary biliary cholangitis (also known as primary biliary cirrhosis)
TE	transient elastography

4. OVERVIEW AND RATIONALE

Study 747-302 is a Phase 4¹, double-blind, placebo-controlled, multicenter study to investigate the effects of obeticholic acid (OCA) in subjects with primary biliary cholangitis (PBC, also called primary biliary cirrhosis), with high risk of liver-related clinical complications.

Liver biopsy is no longer mandatory for diagnosis of PBC; however, biopsies can provide important information to assess the severity of the disease, as well as prognosis, progression, and response to treatment. A paired biopsy substudy was, therefore, recommended by Regulatory Authorities, to further assess clinical outcomes in terms of histological progression to cirrhosis. This addendum² to the 747-302 Study Protocol defines the paired biopsy substudy to assess the effect of OCA versus placebo on the histological severity of disease (fibrosis/cirrhosis) in subjects with PBC. This substudy will also explore the relationship between histological changes in the liver versus clinical, laboratory, and noninvasive measures indicative of progression to cirrhosis in subjects with PBC treated with OCA.

All information including, but not limited to, inclusion/exclusion criteria and study procedures provided in the current approved version of the study protocol should be followed, in addition to the guidance provided below.

5. OBJECTIVES

Primary Objective

- To assess the effect of OCA compared to placebo on the histological severity of PBC by assessing the following:
 - Progression to cirrhosis, in subjects who are noncirrhotic at Baseline
 - Improvement in fibrosis/cirrhosis, in subjects who are cirrhotic at Baseline

Secondary Objectives

- To assess the effect of OCA on the histological changes in the liver
- To assess the relationship between histological changes and measurements (clinical, laboratory, and noninvasive) indicative of progression to cirrhosis in subjects with PBC. Noninvasive measurements include the following:
 - Transient Elastography (TE)
 - Noninvasive scores of liver fibrosis including enhanced liver fibrosis (ELF), and aspartate aminotransferase to platelet ratio index (APRI)

¹ Study 747-302 is considered a Phase 4 study in regions where OCA has received regulatory approval for primary biliary cholangitis (PBC, also called primary biliary cirrhosis), ie, in the US and the EU; in all other regions, this study is considered Phase 3b. In May 2016, the United States Food and Drug Administration (FDA) granted accelerated approval for OCA (Ocaliva) for the treatment of PBC. In December 2016, Ocaliva received Conditional Approval from the European Medicines Agency's Committee for Medicinal Products for Human Use.

² Note: Addendum 1 (dated 18 Jan 2017) to protocol 747-302 is a country-specific addendum.

6. DETAILS OF THE ADDITIONAL PROCEDURES

SUBJECT POPULATION AND STUDY CENTERS

Number of Subjects: This substudy will enroll approximately 45 subjects.

Eligibility:

- Subjects who are participating in the 747-302 study and meet all eligibility criteria in the current version of the main protocol.
 - For subjects who require a baseline biopsy, Screening Visit 1 data should be available, and a preliminary eligibility assessment should be performed, before the baseline biopsy sample is collected.
 - Subjects must remain enrolled in the main protocol to continue participation in biopsy substudy.
- Must provide written informed consent and agree to comply with the requirements of the substudy protocol.
- Is able to safely undergo a liver biopsy, in the opinion of the Investigator.
- Subjects currently enrolled in the study who have not yet presented with signs and symptoms of progression to cirrhosis may also participate, provided a biopsy sample obtained ≤ 6 months prior to Day 0 is available.

Study Centers: All sites participating in the 747-302 study with the capability to perform serial biopsies may participate in this optional substudy.

STUDY PROCEDURES

In addition to the procedures described in Section 7.1 of the main study protocol, the subjects enrolled in the biopsy substudy will also complete biopsy and additional noninvasive fibrosis assessments described in this addendum.

Biopsy

The goal of this substudy is to maximize the availability of data while minimizing the number of biopsies performed. Thus, all subjects who consent to participate in this substudy will undergo a biopsy at Baseline (if none available from ≤ 6 months prior to Day 0) prior to initiating investigational product, and, based on the results of that biopsy, again upon clinical evidence of progression to cirrhosis or at the end of the treatment (EOT) or End of Study (EOS); see [Table 1](#)). This strategy will allow for both histological confirmation of progression to cirrhosis, as well as possible histological improvement following treatment with OCA.

Table 1: Timing of Second Biopsy

If Baseline biopsy result is:	then second biopsy will be obtained at:
Noncirrhotic	
 The time of presentation of clinical signs and symptoms of cirrhosis, or The EOT (if the subject will continue to attend study visits) or EOS visit if no presentation of clinical signs and symptoms of cirrhosis during study, whichever comes first
Cirrhotic	
 EOT (if the subject will continue to attend study visits) or EOS, whichever comes first

EOT = end of treatment; EOS = end of study

Biopsy-Related Assessments:

- **Baseline Biopsy** may be performed at any time after the Screening Visit 1 eligibility criteria have been reviewed and prior to Day 0. If a biopsy was obtained no more than 6 months before Day 0 and slides or sample quantity are sufficient and suitable for baseline reading, a biopsy at Screening need not be repeated. Baseline biopsy must be collected prior to the first dose of the investigational product.
- **Post-treatment Biopsy:** If a subject develops evidence of probable progression to cirrhosis as assessed by the indicators listed below, the post-treatment biopsy will be performed as close as possible to when progression to cirrhosis is determined by the Investigator, and within approximately 3 months of progression. Biopsy reports and available clinical, laboratory, and radiological assessments will be used as a basis for adjudication by the hepatic outcomes adjudication committee to assure that all events of progression to cirrhosis meet predefined criteria and are consistent across sites.
- **EOT or EOS Biopsy:** Biopsy will be performed as part of the EOT/EOS procedures on all subjects who have not already had a post-treatment biopsy based on evidence of the clinical, laboratory, or radiological indicators of progression to cirrhosis during the course of the study. If, for scheduling purposes, a biopsy cannot be completed as part of the EOT/EOS Visit, the biopsy should be scheduled as close as possible to the actual EOT/EOS Visit date.

Non-invasive Fibrosis Assessments:

TE will be performed when a subject develops evidence of probable progression to cirrhosis. In addition, laboratory samples needed to obtain noninvasive scores of liver fibrosis (ELF and APRI) will also be collected at the time a subject develops evidence of probable progression to cirrhosis.

ASSESSMENT OF EFFICACY

Liver Biopsy Instructions and Central Reading of Liver Histology

Full instructions concerning the number and type of samples to be collected at each visit, the sample collection methods, sample processing, labeling, and shipping will be provided by the Sponsor in a study-specific histology manual. Collection supplies will be provided by the central laboratory and will be appropriately assembled for the specific evaluations required at each visit.

Liver biopsies will generally be obtained from the right lobe of the liver as described in a study-specific histology manual. If the initial biopsy was obtained from the left lobe, then subsequent biopsies should be obtained from the left lobe, and vice versa.

All biopsy assessments, including screening and histology efficacy assessments, will be performed by study pathologist/central reader blinded to the treatment group assignment. The biopsies will be graded by a central reader using a pre-defined scoring system. Detailed information related to biopsy scoring will be provided to the central reader by the Sponsor in a study-specific histology manual.

Paired biopsies (Screening/Baseline biopsy and post-treatment [or EOT/EOS] biopsy) will be read by a central reader blinded to the treatment group assignment.

Biopsy Criteria for Progression to Cirrhosis

The following criteria will be used for adjudication of progression to cirrhosis:

- Persistent (ie, 2 consecutive measurements obtained at least 3 months apart) elevation in Fibroscan® TE >16.9 kPa, AND/OR
- Presence of any of the following:
 - Gastroesophageal varices
 - Ascites
 - Radiological evidence of cirrhosis (nodular liver or enlargement of portal vein and splenomegaly)
 - Combined low platelet count (<140,000/mm³), with any of the following criteria:
 - Persistent decrease in serum albumin, OR
 - Elevation in prothrombin time/international normalized ratio (not due to antithrombotic agent use), OR
 - Elevated total bilirubin >2x upper limit of normal

Transient Elastography

TE assessment will be performed at the investigational sites, where the device is available, using the Fibroscan instrument (Echosens, Paris, France), to assess liver fibrosis.

Noninvasive Scores of Liver Fibrosis

ELF score will be calculated using an algorithm that combines serum values of tissue inhibitor of metalloproteinases-1, procollagen type-3 N-terminal propeptide, and hyaluronic acid. Likewise, APRI score will be obtained from serum aspartate aminotransferase and platelet values.

ASSESSMENT OF SAFETY

Safety assessments will be performed as in Section 12 of the main protocol. In addition, the Investigator will document her/his opinion of the relationship of the adverse events (AEs) to liver biopsy using the criteria outlined in [Table 2](#).

Table 2: Relationship of Adverse Events to Liver Biopsy

Relationship	Description
Related	A reaction that follows a reasonable temporal sequence from the liver biopsy; that follows a known or expected response pattern to the liver biopsy.
Not Related	Any event that does not meet the above criteria.

STATISTICAL METHODS**Primary Efficacy Analysis**

For each treatment group, the number and the proportion of subjects with and without biopsy-assessed cirrhosis determined at EOT/EOS will be presented in a shift table from Baseline to the EOT/EOS, separated for two baseline biopsy-assessed cirrhosis status (ie, cirrhosis versus noncirrhosis). For baseline noncirrhotic subjects without an EOT/EOS biopsy, the cirrhosis status will be presented in a shift table from Baseline to the time when a post-treatment biopsy is performed. The proportion of subjects that have cirrhosis status change will be compared between OCA treatment group and placebo group.

In addition, for the subset of subjects who were noncirrhotic at Baseline, Kaplan-Meier estimates of the time to cirrhosis (as assessed by biopsy) will be summarized and graphed by treatment group.

Secondary Efficacy Analyses

The TE, ELF and APRI scores will be summarized by treatment group using descriptive statistics at Baseline and at each on-study evaluation. The change from Baseline and percentage change from Baseline will also be summarized. Baseline is defined as the mean of all available evaluations before treatment. Further details will be specified in the statistical analysis plan.

Determination of Sample Size

Based on the participation of approximately 10% of subjects in the optional biopsy component of the Phase 3 Study 747-301³, a similar percent of subjects are expected to consent to participate in this substudy. With total enrollment anticipated to be 428 subjects, approximately 45 subjects are expected to enroll in this substudy.

Assuming 45 subjects are noncirrhotic at Baseline, the biopsy data from 45 subjects will provide 73% power to detect a difference in the event rate of progression to cirrhosis when OCA event rate is 0.23 (approximately 50% risk reduction); or 59% power to detect a difference in the event rates of progression to cirrhosis when OCA event rate is 0.28 (approximately 45% risk reduction) at a significance level of 0.1 for a one-sided test and placebo group's event rate is 0.5. The above statistical justification is based on the assumptions that the biopsy substudy will have subjects with a close to 1:1 ratio between placebo and OCA arm.

³ A Phase 3, Double Blind, Placebo Controlled Trial and Long Term Safety Extension of Obeticholic Acid in Patients with Primary Biliary Cirrhosis. ClinicalTrials.gov number, NCT01473524.

ADJUDICATION COMMITTEE

Adjudication of progression of cirrhosis will be performed by an independent hepatic outcomes adjudication committee (refer to Section 13.4 in “Adjudication Committee” subsection of the main protocol). All available documentation of progression to cirrhosis, including biopsy reports, will be made available to the adjudicators.

**Clinical Study Protocol 747-302
OBETICHOLIC ACID (OCA)**

**A Phase 4, Double-Blind, Randomized, Placebo-Controlled, Multicenter Study
Evaluating the Effect of Obeticholic Acid on Clinical Outcomes in Subjects
with Primary Biliary Cholangitis**

THE COBALT STUDY

Clinical Outcomes with Obeticholic Acid in Liver Treatment (COBALT)

Addendum 1: 02 Jan 2018

Country-Specific Addendum for Turkey

EudraCT Number: 2014-005012-42

Sponsor

**Intercept Pharmaceuticals, Inc.
[name]
[name]
USA**

[contact]

[contact]

CONFIDENTIAL

The information contained herein is the property of Intercept Pharmaceuticals, Inc. and may not be reproduced, published, or disclosed to others without written authorization of Intercept Pharmaceuticals, Inc.

SPONSOR'S APPROVAL OF THE PROTOCOL ADDENDUM

Reviewed and Approved by:

PPD

PPD
PhD
PPD
Clinical Development
Intercept Pharmaceuticals, Inc.

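### The biopsy substudy's 73% and 59% power treat all of the roughly 45 expected enrollees as noncirrhotic, although the substudy also plans for baseline-cirrhotic subjects; the effect labelled about 50% is 54%

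*Protocol*

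**What the plan says.** All of this is in Addendum 2.

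- **Enrolment.** Section 6, under the subject population heading, says "This substudy will enroll approximately 45 subjects". The sample size paragraph derives the same number from about 10% participation in a total enrolment of 428: "approximately 45 subjects are expected to enroll in this substudy".
- **Population.** The primary objective in Section 5 has two parts. One is "Progression to cirrhosis, in subjects who are noncirrhotic at Baseline". The other is "Improvement in fibrosis/cirrhosis, in subjects who are cirrhotic at Baseline". Table 1 (timing of the second biopsy) has a row for each baseline result, and the primary shift table is to be "separated for two baseline biopsy-assessed cirrhosis status (ie, cirrhosis versus noncirrhosis".
- **Power.** The sample size paragraph reads "Assuming 45 subjects are noncirrhotic at Baseline, the biopsy data from 45 subjects will provide 73% power", where the "OCA event rate is 0.23 (approximately 50% risk reduction". A second scenario gives 59% at an OCA rate of 0.28, labelled about a 45% reduction. Both are "at a significance level of 0.1 for a one-sided test and placebo group's event rate is 0.5", with allocation close to 1:1.

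**The concern.** The figure of 45 does two jobs. It is the expected total, and it is also the number at risk of progressing. Both can be true only if nobody with baseline cirrhosis joins, and in that case one of the two parts of the primary objective has no subjects. Each cirrhotic subject who enrols reduces the sample behind the stated power.

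The effect label points the same way. A reader who takes 73% as the power for halving the risk is reading the power for a somewhat larger effect.

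What is at stake is how the substudy is read. Section 4 of the addendum says regulators recommended it to assess histological progression, and participants undergo repeat liver biopsy for it. Those who judge its value, or interpret a null result, should see power for the sample it is likely to have.

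**Working it through.** **Inputs from the addendum:** placebo rate p1 = 0.50; OCA rate p2 = 0.23 or 0.28; one-sided alpha 0.10 (z = 1.2816); 1:1 allocation; 45 subjects, so n = 22.5 per arm.

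**Formula** (two proportions, pooled variance under the null, no continuity correction):

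power = Φ{ [ (p1 − p2) − z·√(2·p̄(1 − p̄)/n) ] / √( [p1(1 − p1) + p2(1 − p2)]/n ) }, with p̄ = (p1 + p2)/2.

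**Step 1: reproduce the stated figures with n = 22.5 per arm.**

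- p2 = 0.23: p̄ = 0.365; null SE = √(0.46355/22.5) = 0.1435; alternative SE = √(0.4271/22.5) = 0.1378. (0.27 − 1.2816 × 0.1435)/0.1378 = 0.625, so power is **73.4%** (stated: 73%).
- p2 = 0.28: p̄ = 0.39; null SE = √(0.4758/22.5) = 0.1454; alternative SE = √(0.4516/22.5) = 0.1417. (0.22 − 1.2816 × 0.1454)/0.1417 = 0.237, so power is **59.4%** (stated: 59%).

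Both match. The calculation is sound for 45 noncirrhotic subjects; the issue is the number put into it.

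**Step 2: vary the noncirrhotic share.** The addendum gives no share, so the first column is an assumption. The formula is unchanged, with n equal to half the noncirrhotic total.

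| Noncirrhotic share (assumed) | Noncirrhotic subjects | Power, OCA 0.23 | Power, OCA 0.28 |
|---|---|---|---|
| 100% (as stated) | 45 | 73% | 59% |
| 90% | 40.5 | 70% | 56% |
| 80% | 36 | 66% | 53% |
| 70% | 31.5 | 62% | 49% |
| 60% | 27 | 57% | 46% |

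**Step 3: check the effect labels.**

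- 1 − 0.23/0.50 = 0.54, a 54% reduction, labelled about 50%.
- 1 − 0.28/0.50 = 0.44, a 44% reduction, labelled about 45%; this is acceptable rounding.
- A true 50% reduction means p2 = 0.25. With n = 22.5: p̄ = 0.375; null SE = √(0.46875/22.5) = 0.1443; alternative SE = √(0.4375/22.5) = 0.1394. (0.25 − 1.2816 × 0.1443)/0.1394 = 0.466, so power is **68%** with all 45 noncirrhotic. With 70% noncirrhotic it is 57%.

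The label is therefore worth about 5 points (73% against 68%).

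**The case against.** The strongest reply is that nothing is hidden or miscalculated. The sentence opens with its condition, and under that condition both figures are right. That stands, and it settles what kind of fault this is: a reader might infer an arithmetic error, but Step 1 rules that out. It does not remove the inconsistency, because the stated condition leaves no subjects for the second part of the substudy's own primary objective, and no other case is shown.

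Second, power did not set the sample size. The 45 comes from expected consent, the substudy is optional, and the main trial's endpoint, alpha and 127-event target are untouched. This stands in full and limits the severity.

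Third, the addendum already presents a modest test, with one-sided alpha 0.10 and 59% power in its second scenario. There is also some reason to expect many noncirrhotic subjects: those already in the study may join only if they have not yet shown signs of progression to cirrhosis, and the amended ALP criterion admits earlier disease. The same amendment raised the bilirubin ceiling, however, so the share is unknown in either direction.

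Fourth, the label says approximately and both rates are printed, so a careful reader can see the 54%. That is fair; the label is the lesser point.

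**Conclusion.** The point holds as an inconsistent best-case assumption. The 73% and 59% are upper bounds, reached only if every enrollee is noncirrhotic with paired biopsies. The direction of the shortfall is certain once any cirrhotic subject enrols. Its size depends on a share the addendum does not give: over an assumed 90 to 60% noncirrhotic, power is 70 to 57% at 0.23 and 56 to 46% at 0.28. The label correction is separate and firm: 54%, with 68% power for a true 50% reduction at n = 45.

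Three stronger readings are tempting, and the documents do not support them.

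- **That the test is close to a coin toss.** This rests on assumed shares; at 0.23, power is still 57% with only 60% noncirrhotic.
- **That the main trial's 10% dropout should be taken off as well.** That figure belongs to the main trial's sample size. In the substudy, stopping treatment or leaving the study is itself an occasion for the second biopsy. Some biopsies will be missed, but their number is not the dropout rate.
- **That an exact test would show still lower power, so the stated figures are inflated.** The addendum names no test, and the figures are right for the usual uncorrected comparison.

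Severity is minor to should-fix: the substudy is optional, its size was set by expected consent, and the main analysis does not depend on it.

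**What to change.** Revise the sample size paragraph of Addendum 2.

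1. State power by number of baseline-noncirrhotic subjects with paired biopsies, for example n = 45, 40, 36, 32 and 27, and mark 45 as the upper bound.
2. Either relabel 0.23 as a 54% reduction, or quote 68% power for a 50% reduction (0.25) with all 45 noncirrhotic.
3. If missing second biopsies are to be allowed for, show them as a labelled assumption and do not carry over the main trial's dropout rate.

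The cost is one paragraph and a less favourable stated power. Enrolment, biopsy schedule and analyses need not change.

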1. OVERVIEW AND RATIONALE

The purpose of this Country-Specific Protocol Addendum (dated 02 Jan 2018) is to revise the study phase from Phase 4 to Phase 3b in Turkey for Protocol 747-302. Obeticholic acid (OCA) has received regulatory approval in a number of regions (United States, European Union, and Canada) for the treatment of PBC in combination with UDCA in adults with an inadequate response to UDCA or as monotherapy in adults unable to tolerate UDCA. Based on this regulatory approval, the phase of the 747-302 study changed to Phase 4 with Protocol Version 4 to reflect that this study is now considered a post-marketing study in these regions, where the majority of participating sites and countries in the 747-302 study are also located. However, as OCA has not yet received regulatory approval in Turkey, this addendum was issued to document that Study 747-302 is considered a Phase 3b study in Turkey.

The following referenced sections of the protocol reflect this change:

Title Page and Synopsis, Title of Study: A Phase 3b, Double Blind, Randomized, Placebo Controlled, Multicenter Study Evaluating the Effect of Obeticholic Acid on Clinical Outcomes in Subjects with Primary Biliary Cholangitis

Synopsis, Phase of Development: 3b

Synopsis, Methodology:

This Phase 3b, double-blind, randomized, placebo-controlled, multicenter study will evaluate the effect of OCA on clinical outcomes in subjects with PBC.

Section 7.1, Overall Study Design

This is a Phase 3b, double-blind, randomized, placebo-controlled, multicenter study.

A copy of this addendum should be filed alongside the current approved version of the study protocol at all investigative sites in Turkey. All information including, but not limited to, inclusion/exclusion criteria and study procedures provided in the current approved version of the study protocol should continue to be followed.
